10.3 Secondary Outcome Measures - Precursors to Community Ambulation

10.3.1 Endurance

To assess endurance, the SMWT (described above) will be used to obtain a continuous measure of total distance walked in six minutes.¹⁵⁸ The SMWT is highly correlated with workloads, heart rate, oxygen saturation, and dyspnea responses when compared to bicycle ergometry and treadmill exercise tests in older persons.^{105,156,158} It has been performed by elderly, frail and severely compromised participants who cannot perform standard maximal treadmill or cycle ergometry exercise tests.^{31,159}

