10.3.5 Fast Walking Speed

Within the mPPT, participants are asked to walk a distance of 50 feet walking quickly but safely. The time required to walk 50 ft will be the measure of fast walking speed.

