11.5 Primary Outcome Classification

At baseline, all participants will, by design, be tested at the clinical site. At the follow-up visit, we will attempt to test all participants at the clinical site. When this is not possible, we will attempt to have study staff administer the test in a non-study clinical facility or, failing that, at another non-study location or the participant's home. All cases for which, despite intensive efforts, administration of the SMWT is not possible will be submitted for adjudication. See Figure 4.

Although there is an absence of highly sensitive and specific surrogate measures for the ability to walk ≥ 300 m in six minutes, prior studies suggest that there are factors that are highly predictive of the *inability* to walk at that speed. Therefore, the purpose of the adjudication will be to reduce the number of participants with missing outcomes by identifying treatment failures in cases where the SMWT could not be administered. Based on the adjudication, participants who meet one or more of the following criteria at the follow-up assessment will be classified as treatment failures in the primary analysis for the given follow-up time:

- 1) Participant died
- 2) Participant was too sick, based on adjudicators' review of source documentation, to walk 300 m or more in six minutes
- 3) Gait speed based on SPPB four-meter walk was less than 0.6 m/s (very slow speed incompatible with ability to walk 300 m in six minutes)
- 4) Participant or proxy reports (a) participant limitation in walking several blocks or (b) in walking across a small room without help from another person

[figure not shown]
Criterion 4a is an item from the Activity Limitations section of the SF-36 and was chosen because, in a previous hip fracture study performed by our group, 100% of 27 participants meeting the criterion were unable to walk 300 m or more in six minutes (unpublished data). Also, in that study, 85% of 26 participants who had a missing SMWT reported this level of walking limitation, suggesting that use of this item will allow us to assign a classification to a large proportion of those who were not tested on the SMWT. Criterion 4b is an item from the Pepper Assessment Tool for Disability and was chosen because it has high face validity for predicting treatment failure. To improve our ability to classify the outcome status of participants whose SMWT was not administered, we will make intensive efforts to obtain self- or proxy-

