1.2.2 Secondary and Tertiary Outcomes

Secondary outcomes include five variables (endurance, dynamic balance, walking speed, quadriceps strength, and lower extremity function) that are hypothesized to be precursors to community ambulation. In addition, we will examine the difference between the treatments with respect to the following tertiary outcomes: ADLs, balance confidence, quality of life, physical activity, lower extremity physical performance, depressive symptoms, increase of ≥ 50 meters in distance walked in six minutes, cognitive status, and nutritional status.

With the exception of “increase of 50 meters in distance walked in six minutes”, these variables are quantitative. Prior to analyzing the relationship between treatment and the quantitative variables we will use histograms and side-by-side box plots to examine the shape of the distributions and identify potential outliers. If the data strongly depart from normality, we will consider transforming the data or using rank-based methods for the analyses described below.

Mixed effects models fit by restricted maximum likelihood will be used to compare the PUSH and PULSE interventions at 16 and 40 weeks post-randomization with respect to each outcome. Increase of ≥ 50 m in distance walked, a dichotomous outcome, will be analyzed using the same method as the primary outcome. All of the other secondary and tertiary outcomes are continuous; therefore, a normal model will be used to estimate the parameters in the following equation:

$$\mu_{ij} = b_0 + b_1 t_{16_{ij}} + b_2 t_{40_{ij}} + b_3 X_i t_{16_{ij}} + b_4 X_i t_{40_{ij}}, \quad (\text{Eq. 2})$$

where μ_{ij} is the mean of the j th outcome from the i th participant, X_i is the intervention indicator (1/0) variable; $t_{16_{ij}}$ and $t_{40_{ij}}$ are the 16- and 40-week follow-up time post-randomization indicators, respectively; and $X_i t_{16_{ij}}$ and $X_i t_{40_{ij}}$ are the intervention-by-time interaction variables.

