1.4 Missing Data

By design, there will be no missing data at baseline because only participants with complete baseline data will be randomized. At follow-up, scores for scales that have published rules for handling missing scale items (e.g., the CES-D and the SF-36) will be calculated using those rules. If necessary, the PAT-D and each of its subscales will be prorated based on nonmissing items. However, the whole scale will be considered missing if more than 30% of its items are missing. Similarly, each of the subscales will be missing if more than 30% of the subscale items are missing. If necessary, the mPPT will be prorated based on nonmissing items. However, the scale will be considered missing if three or more of the tasks were not done because of technical issues (e.g., no stairs available for stair climbing task). All other scales will be considered missing if any part of the scale is missing. As a secondary analysis, to correct for imbalances due to chance or differential missing data, we will adjust for covariates in our models. Candidate variables that will be adjusted for are age, sex, and type of hip fracture; baseline BMI, MNA[®]-SF score, CES-D score, 3MS score, distance walked in six minutes on SMWT, SPPB score, mPPT score, NHATS balance score, gait speed on 50-ft fast walk, and gait speed on 4-m usual walk; and the presence of cardiac disease, pulmonary disease, diabetes, and history of stroke or TIA at baseline. As described above, these variables will be ranked for inclusion as adjustment variables using the Beach-Meier approach (Beach 1989). We will adjust for the same number of covariates in this analysis as in the analysis described in

above for covariate adjustment for the analysis of our primary outcome. This approach will result in unbiased estimates if the missingness is at random, conditional on the covariates.

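### Death and sickness count as failure in the primary analysis, but six-minute distance and timed gait speed have no rule for these participants and no analysis beyond missing at random

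*SAP*

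**What the plan says.** For the primary outcome, Protocol 11.5 states that "participants who meet one or more of the following criteria at the follow-up assessment will be classified as treatment failures in the primary analysis". The criteria are death, being too sick, a slow 4-metre walk, and a reported walking limitation (several blocks, or crossing a small room without help). SAP 1.1.1 carries this over.

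For the continuous outcomes the plan defines a measurement but no value when it cannot be made. Under Protocol 10.3.1 the walk test "will be used to obtain a continuous measure of total distance walked in six minutes". Under Protocol 10.3.5, "The time required to walk 50 ft will be the measure of fast walking speed". SAP 1.2.2 says that "Mixed effects models fit by restricted maximum likelihood will be used to compare the PUSH and PULSE interventions", with baseline treated as an outcome and an unstructured covariance. Rank-based methods appear there only as an option if the data are far from normal.

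SAP 1.4 adds a covariate-adjusted secondary analysis and says of it: "This approach will result in unbiased estimates if the missingness is at random, conditional on the covariates". The sensitivity analysis for data missing not at random is in SAP 1.1.2, under the primary outcome.

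SAP 1.3 makes the cost-effectiveness analyses depend on a significant primary result, or on a significant and clinically meaningful difference in any of four measures: six-minute distance (50 m), 50-ft and 4-m gait speed (0.10 m/s each) and SPPB (1.0).

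**The concern.** The same participant can have a known bad outcome in one analysis and no outcome in another. A likelihood model fitted to observed values does not ignore such a participant, because the baseline value stays in. But it implicitly assigns a follow-up course like that of similar participants who were tested. For someone who died or cannot walk, that course describes a state that did not occur. The covariate-adjusted analysis rests on the same kind of assumption, so it cannot show whether the result depends on it.

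Two things are at stake. If death or inability is unevenly spread between the arms, distance and gait speed can tell a different story from the primary outcome only because of how these participants are handled. And these measures can open the cost-effectiveness analyses when the primary test does not.

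**Working it through.** **1. The plan's own figures.**
- Detectable effect (Protocol 15.6.2): n per arm = 105 × (1 − 0.068) = 97.86; d = (1.960 + 0.842) × √(2/97.86) / 0.878 = 0.456 SD. The protocol states 0.46, so this figure reproduces and is not in question.
- Distance scale (Protocol 15.6.1): 50 m is 0.6 SD, so SD = 50/0.6 = 83.3 m. With 16% of PULSE above 300 m, the PULSE mean = 300 − 0.9945 × 83.3 = 217.1 m. Check: 1 − Φ(0.9945 − 0.6) = 34.7%, a gain of 18.7 points, which matches the stated 19.

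**2. The rules side by side, for a participant without a walk test.**

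| Reason | Primary outcome | Six-minute distance | Timed gait speed |
|---|---|---|---|
| Died | failure | no value | no value |
| Too sick | failure | no value | no rule if not done |
| 4-m speed below 0.6 m/s | failure | no value | 4-m speed observed |
| Reported limitation | failure | no value | as observed, otherwise no rule |

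The third row follows from the criterion itself: "Gait speed based on SPPB four-meter walk was less than 0.6 m/s".

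**3. Size for distance.** Assumptions: a 50 m effect among those who can be tested, and shares f of 2 to 7% per arm who died or could not walk (the documents give no such share). Zero is used only to show the contrast. If inability is unrelated to baseline, the missing-at-random estimate is 50 m. The contrast is (1 − f_PUSH) × 267.1 − (1 − f_PULSE) × 217.1.

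| f PUSH | f PULSE | Difference (m) | Shift from 50 m |
|---|---|---|---|
| 2% | 2% | 49.0 | −1.0 |
| 5% | 5% | 47.5 | −2.5 |
| 3% | 7% | 57.2 | +7.2 |
| 7% | 3% | 37.8 | −12.2 |
| 2% | 7% | 59.9 | +9.9 |
| 7% | 2% | 35.6 | −14.4 |

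With equal shares the shift is −f × 50, so at 7% it is −0.07 × 50 = −3.5 m.

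**4. Check with inability linked to baseline.** A simulation used a baseline-adjusted regression in place of the mixed model, an assumed baseline correlation of 0.6, and inability more likely at low baseline. The missing-at-random model then predicts on average about 180 to 205 m for those unable. The difference moves from 49.8 to 47.4 m at 5%/5% (PUSH/PULSE), from 50.2 to 55.5 m at 3%/7% and from 50.1 to 39.9 m at 7%/3%. The shifts are somewhat smaller than in step 3, with the same signs.

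**5. Two neighbouring rules.**
- mPPT: with four of nine tasks undone and a mean of 3 on the other five, scoring the undone tasks 0 gives 15, and proration gives 15 × 9/5 = 27. The reading matters.
- 50 m gain: 0.6 m/s × 360 s = 216 m, and 216 − 50 = 166 m. A participant starting below 166 m can be a 300 m failure on the speed criterion and still have gained 50 m.

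**The case against.** The strongest reply is that the protocol's evidence on untested participants does not show that the model's predictions are wrong for most of them. Protocol 11.5 reports that "85% of 26 participants who had a missing SMWT reported this level of walking limitation" and that all 27 participants with that limitation were unable to reach 300 m. But the limitation concerns several blocks, and by the plan's own assumption 84% of PULSE participants also fall short of 300 m. A prediction near 200 m is compatible with that. This stands: the argument applies to deaths and to people who truly cannot walk, not to everyone classed as a failure.

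Second, giving the dead the worst value is a choice of estimand, not the correction of an error, and the sentence quoted from SAP 1.4 is a correct conditional statement about a secondary analysis. It does not declare deaths to be missing at random. This also stands, and it is why the remedy should be supportive. It does not answer the absence of any rule for these participants, or of any analysis outside that assumption.

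Third, a reader might infer from "the scale will be considered missing if three or more of the tasks were not done because of technical issues" that known inability on the mPPT is replaced by prorated values. The text does not establish that. Items run from 0 to 4, SPPB and balance items score inability as 0, and the only reason given for undone tasks is technical. The wording fits a reading in which inability scores 0 and only technical omissions are prorated.

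Fourth, analysing the 50 m gain by the primary outcome's method may mean only the same statistical test, without carrying over the 300 m failures.

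**Conclusion.** The gap is real for six-minute distance and the timed gait speeds: no rule after death or inability, reliance on missing at random in both planned analyses, and a sensitivity analysis confined to the primary outcome. For 4-m speed it is narrower, because failures on the speed criterion have an observed value.

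Direction and size cannot be settled from the documents. Under the assumed shares of 2 to 7%, the distance difference moves by about 1 to 3.5 m if the arms are equal, and by about 10 m (more in PULSE) to 14 m (more in PUSH) if they differ by 5 points. A result near 50 m could therefore change sides of the threshold.

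It is tempting to size the effect from the 6.8% loss to follow-up or the 10% indeterminate at week 40. Neither measures death or inability, and indeterminate participants are by definition those not adjudicated as failures. Nor do the documents show that one particular arm is favoured. The mPPT and 50 m points are clarifications, not demonstrated errors.

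**What to change.** Add to SAP 1.2.2 and 1.4 a pre-specified supportive rank-based comparison of six-minute distance and both gait speeds:
- Rank deaths lowest, then participants adjudicated too sick or reported unable to cross a small room without help, then observed values.
- Keep the observed 4-m speed for participants who failed on the speed criterion.
- Do not assign zero to participants who report only a limitation in walking several blocks.
- Report whether the decision to run the cost-effectiveness analyses changes.

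Two clarifying sentences should go with it. First, mPPT tasks not done through inability score 0, and proration applies only to technical omissions. Second, for the 50 m gain, death counts as no, and 300 m failures based on 4-m speed or on the several-blocks item are not carried over automatically.

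The cost is a few sentences and one table. Reasons for a missing walk test are already reviewed at adjudication. Adjudication does not cover 50-ft walks or mPPT tasks left undone, so those reasons must come from the assessment records. The composite mixes survival with function, so it should remain supportive of the mixed model and not replace it.

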1.5 Accounting for Variability

To address the possibility that variation between physical therapists could affect the findings, we will rerun the analyses including a random effect for physical therapist. Also, to account for variability between clinical sites, we will run analyses including a random effect for site.

References

Chan, I. S. F. and Zhang, Z. (1999), “Test-Based Exact Confidence Intervals for the Difference of Two Binomial Proportions,” *Biometrics*, 55, 1202–1209

Magder LS, *Controlled Clinical Trials*, 2003 Aug;24(4):411-21.
